### 8.7.3. Impact of sample size on holding rule assessment

The likelihood that a particular holding rule is met varies according to the total number of subjects expected to be evaluated at the time of an iSRC review. With 37 enrolled subjects and a cut off of 8/37, there is 90% chance that the holding rule 2b/2c is met for a vaccine with a true incidence rate of an event triggering a holding rule of 30%,

representing an unacceptable safety profile, and 95 % chance that the holding rule is not met for a vaccine with a true incidence of 10%. Refer to [Figure 2](#).

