### 1.3. Rationale for the study design

This study will assess the balance between immune responses and adverse effects associated with different amounts of AS03 adjuvant and Q-Pan H5N1 antigen in combination. In previous pediatric studies, 1.9 µg HA combined with AS03B was highly immunogenic and had an acceptable safety profile [Kosalaraksa, 2015]; it has therefore been defined as the reference dose for this study. Alternative doses will include 0.9 µg, 1.9 µg, or 3.75 µg HA in combination with AS03C (approximately one-fourth the adult dose of AS03) or 3.75 µg HA antigen in combination with AS03D (approximately one-eighth the adult dose of AS03).

The schedule for the priming regimen in this study (2 doses, 21 days apart) is consistent with the schedule used in all prior pediatric studies.

The study will plan to enrol 37 children per group to achieve 34 evaluable subjects per group with an overall target of 185 children. Power calculations are given in Section 10.3.

Experience with D-Pan H5N1 vaccines suggests that fever, in addition to being objectively measurable, is a relevant parameter indicative of reactogenicity in children below 6 years of age. Accordingly, this study will use fever (defined as a body temperature  $\geq 38^{\circ}\text{C} / 100.4^{\circ}\text{F}$ ) by any route; axillary is preferred in this study) within 3 days after each dose to assess the balance between reactogenicity and immunogenicity. This will be evaluated via immunogenicity-fever indices constructed using Day 42 immune response either by hemagglutination inhibition (HI) assay or by microneutralization (MN) assay and reactogenicity as assessed by fever score.

The 6 – 35 month age group, which has had both the highest rates of fever and the highest post-vaccination antibody titers in previous clinical trials, will be studied. Reactogenicity and immune response in this age group will inform dose selection across the entire pediatric population.

For a pandemic vaccine, which might have to protect against a second or third wave of H5N1 infections, the quality and persistence of the immune response after priming are important parameters.

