**Table 20 Holding Rules**

Holding Rule #	Event	# of subjects	Proportion of subjects
1a‡	If one subject experiences death or a life-threatening event	≥ 1	
1b‡	If one subject experiences any vaccine-related* SAE	≥ 1	
1c‡	If one subject is diagnosed with a potential immune-mediated disease	≥ 1	
1d†	If one subject is withdrawn from the study (by investigator request) following a Grade 3 vaccine-related AE*	≥ 1	
1e†	Any vaccine-related* local or general solicited AE leading to hospitalization, or vaccine-related* fever >40°C by any route, or necrosis at the injection site, within the 7-day post-vaccination period	≥ 1	
2a	Subjects reporting any Grade 3 solicited local AE in an investigational group, within the 7-day post-vaccination period		≥ 30%
2b	Subjects reporting any Grade 3 vaccine-related* solicited general AE in an investigational group, within the 7-day post-vaccination period		≥ 20%
2c	Subjects reporting any Grade 3 vaccine-related* unsolicited AE in an investigational group, within the 21-day post-vaccination period		≥ 20%

‡ Reported via eCRF within 24 hours

\* vaccine related implies that there is a reasonable possibility that the vaccine(s) contributed to the SAE/AE as determined by the Investigator.

[figure not shown]
† Investigators should refer to the local study contact information document to notify the study sponsor within 24 hours of any 1d or 1e events.

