**Figure 2 Probability to conclude that a specific formulation is safe according to safety holding rule 2 with N = 37**

## **9. SUBJECT COMPLETION AND WITHDRAWAL**

### **9.1. Subject completion**

A subject who returns for the concluding visit/is available for the concluding contact foreseen in the protocol is considered to have completed the study.

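### Protocol 8.7.3 gives a 95% chance that holding rule 2b/2c is not met at 10% incidence; with the stated 8/37 cut-off the exact value is 97.3%

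*Protocol*

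**What the plan says.** Table 20 (Section 8.7.2) suspends further priming doses, pending a safety review, when a set proportion of a group has a given type of event. Rule 2b counts "Subjects reporting any Grade 3 vaccine-related* solicited general AE in an investigational group, within the 7-day post-vaccination period"; rule 2c counts Grade 3 vaccine-related unsolicited events within 21 days. Both have a threshold of at least 20% of subjects.

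Section 8.7.3 then gives the operating characteristics at full group size. For a true incidence of 30%, described as unacceptable, it says: "With 37 enrolled subjects and a cut off of 8/37, there is 90% chance that the holding rule 2b/2c is met". For the acceptable case it gives a "95 % chance that the holding rule is not met for a vaccine with a true incidence of 10" per cent. It refers the reader to Figure 2, titled "Probability to conclude that a specific formulation is safe according to safety holding rule 2 with N = 37". No calculation method is stated.

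**The concern.** The number of subjects, the cut-off and the true incidence are all given in the sentence, so the probability is determined without any outside figure. The stated 95% does not follow from those inputs, although its companion 90% does.

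The figure tells a reader how often the rule would stop dosing for a formulation with a tolerable event rate. A 95% chance of not holding implies a 5% chance of an unnecessary hold; the exact chance is a little over half of that. Anyone weighing the rule's false-hold risk against its ability to catch a 30% rate would be using a wrong number for one side of that trade-off.

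**Working it through.** **Inputs**
- Group size: n = 37 (Section 8.7.3).
- Threshold for rules 2b and 2c: at least 20% (Table 20).
- Cut-off: 8 of 37 (Section 8.7.3). This agrees with Table 20, since 7/37 = 18.9% falls short of 20% and 8/37 = 21.6% reaches it. The rule is therefore met when X ≥ 8, with X the number of children with an event.
- True incidences: 30% and 10% (Section 8.7.3).

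**The figure that reproduces.** With X ~ Binomial(37, 0.30):

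P(met) = P(X ≥ 8) = 1 − P(X ≤ 7) = 1 − 0.0947 = 0.9053.

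This is 90.5%, in line with the stated 90%, and it confirms the reading X ≥ 8.

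**The figure that does not.** With X ~ Binomial(37, 0.10):

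P(not met) = P(X ≤ 7) = Σ C(37, k) × 0.10^k × 0.90^(37−k), for k = 0 to 7.

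| k | P(X = k) |
|---|---|
| 0 | 0.0203 |
| 1 | 0.0834 |
| 2 | 0.1667 |
| 3 | 0.2161 |
| 4 | 0.2041 |
| 5 | 0.1497 |
| 6 | 0.0887 |
| 7 | 0.0436 |
| Sum | 0.9726 |

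So the chance that the rule is not met is 97.3%, against 95% stated (97.26 − 95 = 2.26 points). The chance of a hold is 1 − 0.9726 = 2.7%, against an implied 5%.

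**Could another calculation have produced the stated pair?**

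| Variant | Not met at 10% | Met at 30% |
|---|---|---|
| Stated in 8.7.3 | 95% | 90% |
| Exact, 8/37 | 97.3% | 90.5% |
| Exact, 7/37 | 92.9% | 95.6% |
| Exact, 9/37 | 99.1% | 82.4% |
| Exact, 7/34 | 95.2% | 92.1% |
| Poisson, 8/37 | 96.5% | 86.3% |
| Normal, evaluated at 7 | 96.5% | 92.9% |
| Normal, evaluated at 7.5 (continuity correction) | 98.1% | 90.2% |
| Normal, evaluated at 8 | 99.1% | 86.7% |

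The normal rows use mean 3.7 and SD √3.33 = 1.825 at 10%, and mean 11.1 and SD √7.77 = 2.787 at 30%. The Poisson row uses means 3.7 and 11.1.

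No row gives both stated figures. The nearest for the 95% is 7/34, which uses the 34 evaluable children per group planned in Section 1.3 (20% of 34 is 6.8, so 7 is the first count to qualify). However, that row gives 92.1% at 30% incidence, and neither its group size nor its cut-off is the one stated.

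Solving P(X ≤ 7 | 37, p) = 0.95 gives p = 0.112. With the 8/37 cut-off, a 95% chance of not holding therefore belongs to a true incidence of 11.2%, not 10%.

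**The case against.** The best defence is that 90% and 95% are conventional benchmarks in a descriptive sentence, not exact values. Read as floors, both are true: 90.5% exceeds 90% and 97.3% exceeds 95%. But the sentence does not say "at least". It gives two point values in parallel, one of which is the rounded exact value. Elsewhere the protocol writes bounds as bounds, with inequality signs in Tables 22 and 23. The floor reading is a fair guess at what was intended, but it is not what the text says.

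Second, Figure 2 was not visible in the text reviewed and may well plot the right value. If so, the fault is confined to the prose. That narrows the error but does not make the sentence correct.

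Third, nothing depends on the number. The 8/37 cut-off follows from the 20% threshold, not from the 95%. Meeting the rule only suspends dosing until safety data are reviewed, and the figure that protects children, detection of a 30% rate, is right. Section 8.7.3 also notes that the probabilities vary with the number of subjects available at each review, so n = 37 is only one reference point. All of this stands, and it is why the point is minor. It bears on the importance of the error, not on whether there is one.

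**Conclusion.** The concern holds, as a minor arithmetic error. With 37 subjects and a cut-off of 8, the chance that rule 2b/2c is not met at a true incidence of 10% is 97.3%, not 95%: a difference of 2.3 percentage points. The chance of an unnecessary hold is overstated, at 5% implied against 2.7% exact, so the error is conservative.

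The result rests only on the inputs in Section 8.7.3 and Table 20, and on the usual binomial assumption that children in a group have independent events with a common probability. That same assumption reproduces the protocol's 90%. The conclusion says nothing about Figure 2 and does not touch the rule, the cut-off, the sample size or the 90% figure.

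**What to change.** In Protocol Section 8.7.3, replace 95% by 97% (exact value 97.3%). Check that Figure 2 shows the same value at 10% incidence, and correct it if it does not. The cost is one number in the text; the rule, cut-off, sample size and study conduct stay as they are.

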**Figure 2 Probability to conclude that a specific formulation is safe according to safety holding rule 2 with N = 37**

## **9. SUBJECT COMPLETION AND WITHDRAWAL**

### **9.1. Subject completion**

A subject who returns for the concluding visit/is available for the concluding contact foreseen in the protocol is considered to have completed the study.

### **9.2. Subject withdrawal**

Withdrawals will not be replaced.

#### **9.2.1. Subject withdrawal from the study**

From an analysis perspective, a ‘withdrawal’ from the study refers to any subject who did not come back for the concluding visit/was not available for the concluding contact foreseen in the protocol.

All data collected until the date of withdrawal/last contact of the subject will be used for the analysis.

A subject is considered a ‘withdrawal’ from the study when no study procedure has occurred, no follow-up has been performed and no further information has been collected for this subject from the date of withdrawal/last contact.

Investigators will make an attempt to contact those subjects who do not return for scheduled visits or follow-up.

Information relative to the withdrawal will be documented in the eCRF. The investigator will document whether the decision to withdraw a subject from the study was made by the subject’s parent(s)/LAR(s) or by the investigator, as well as which of the following possible reasons was responsible for withdrawal:

- Serious adverse event.
- Non-serious adverse event.
- Protocol violation (specify).
- Consent withdrawal, not due to an adverse event\*.
- Moved from the study area.
- Lost to follow-up.
- Other (specify).

\*In case a subject is withdrawn from the study because the subject’s parent(s)/LAR(s) has/have withdrawn consent, the investigator will document the reason for withdrawal of consent, if specified by the subject/subject’s parent(s)/LAR(s), in the eCRF.

Subjects who are withdrawn from the study because of AEs must be clearly distinguished from subjects who are withdrawn for other reasons. Investigators will follow subjects who are withdrawn from the study as result of an AE until resolution of the event (see Section 8.4.2).

### **9.2.2. Subject withdrawal from investigational vaccine**

A ‘withdrawal’ from the investigational vaccine refers to any subject who does not receive the complete treatment, i.e. when no further planned dose is administered from the date of withdrawal. A subject withdrawn from the investigational vaccine may not necessarily be withdrawn from the study as further study procedures or follow-up may be performed (safety or immunogenicity) if planned in the study protocol.

Information relative to premature discontinuation of the investigational vaccine will be documented on the Vaccine Administration page/screen of the eCRF. The investigator will document whether the decision to discontinue further vaccination/treatment was made by the subject’s parent(s)/LAR(s), or by the investigator, as well as which of the following possible reasons was responsible for withdrawal:

- Serious adverse event.
- Non-serious adverse event.
- Other (specify).

## **10. STATISTICAL METHODS**

### **10.1. Primary Endpoints**

See [glossary of terms](#) for definitions of SPR, GMT.

#### **10.1.1. Immunogenicity-fever indices**

Separate HI and MN immunogenicity-fever indices will be constructed based on the following endpoints:

- Humoral immune response in terms of vaccine-homologous HI antibody for each group:
  - LL (lower limit) of 95%CI of GMT group ratio at Day 42 using 1.9 µg HA with AS03B as reference
- Humoral immune response in terms of vaccine-homologous MN antibodies for each group:
  - LL of 95%CI GMT group ratio at Day 42 using 1.9 µg HA with AS03B as reference
- Fever measurement ( $\geq 38^{\circ}\text{C}$ ) post dose 1 and dose 2
  - For each subject, a fever index will be calculated using temperature measurements 3-days post Dose 1 (D0-D2) and 3-days post Dose 2 (D21-D23)

For details regarding construction of these indices refer to Section [10.6.2.1](#).

### **10.1.2. Immune response to a booster dose**

Following booster dose administered at Day 385 the following will be evaluated:

- For immune response in terms of HI antibodies against vaccine-homologous antigen
  - Mean Geometric Increase (MGI) at Day 392 relative to Day 385
- For the immune response in terms of MN antibodies against vaccine-homologous antigen
  - MGI at Day 392 relative to Day 385

## **10.2. Secondary Endpoints**

### *Immunogenicity*

- For humoral immune response in terms of HI antibodies against vaccine-homologous/heterologous antigens post primary immunization, the following aggregate variables will be calculated for each group:
  - Seroconversion rates (SCR) at Day 42
  - Seroprotection rates (SPR) at Day 42
  - MGI at Days 42 relative to Day 0
- For humoral immune response in terms of vaccine-homologous MN antibody post the primary immunization, following aggregate variables will be calculated for each group. :
  - MGI at Day 385 relative to Day 0
- For humoral immune response in terms of HI antibodies against vaccine-homologous/heterologous antigens (at Days 0, 42 and 385 post the primary immunization, at Day 392 (7 days post booster dose)), the following aggregate variables will be calculated for each group:
  - Seropositivity rates at Days 0, 42, 385 and Day 392
  - Seroconversion rates (SCR) at Day 385 (relative to Day 0) and Day 392 (relative to Days 0 and 385)
  - Seroprotection rates (SPR) at Days 0, 385 and Day 392
  - Geometric Mean Titer (GMT) at Days 0, 42, 385 and Day 392
  - MGI at Day 385 (relative to Day 0), MGI at Day 392 (relative to Days 0 and 385)
- For humoral immune response in terms of vaccine-homologous/**heterologous** MN antibody, the following aggregate variables will be calculated for each group  
*(Amended: 27-MAR-2017)*:
  - Seropositivity rates at Days 0, 42,385 and Day 392

- GMT at Days 0, 42,385 and Day 392
- Vaccine response rate (VRR) at Days 42, 385 (relative to Day 0) and Day 392 (relative to Days 0 and 385)

- For CMI in terms of frequencies of antigen-specific cells(CD3+/CD4+/CD8+) at Days 0, 42, 385 and 392:
  - Frequencies of cytokine CD4+/CD8+ T-cells per million CD4+/CD8+ cells producing two or more markers within CD40L, IL-2, TNF- $\alpha$ , IFN- $\gamma$  upon *in vitro* stimulation using A/Indonesia/05/2005 (H5N1) split virus as determined by ICS in a sub-cohort of approximately 20 subjects per group at Days 0, 42, 385 and Day 392

*Reactogenicity /Safety:*

- Solicited local and general AEs
  - Occurrence of each solicited local AEs during a 7-day follow-up period (i.e., day of vaccination and 6 subsequent days) after any vaccination.
    - Percentage, intensity and duration of solicited local AEs during a 7-day follow-up period (Day 0-Day 6) after any vaccination.
  - Occurrence of each solicited general AEs during a 7-day follow-up period (i.e., day of vaccination and 6 subsequent days) after any vaccination.
    - Percentage, intensity, duration and relationship to vaccination of solicited general AEs during a 7-day follow-up period (Day 0-Day 6) after any vaccination.
- Unsolicited adverse events (AEs)
  - For the primary series: occurrence and relationship to vaccination of unsolicited AEs within 21 days after each vaccine dose.
    - Percentage, intensity and relationship to vaccination of unsolicited AEs during a 21-day follow-up period (Day 0-Day 20) after each vaccine dose.
  - For the booster dose [unadjuvanted]: occurrence and relationship to vaccination of unsolicited AEs within 30 days after vaccination
    - Percentage, intensity and relationship to vaccination of unsolicited AEs during a 30-day follow-up period.
  - Occurrence and relationship to vaccination of adverse events with MAEs during the entire study period.
    - Percentage and relationship to vaccination of MAEs during the entire study period.
  - Occurrence and relationship to vaccination of pIMDs, SAEs, AESIs during the entire study period.
    - Percentage and relationship to vaccination of pIMDs, SAEs, AESIs during the entire study period.

### 10.3. Determination of sample size

One of the objectives of the study is to assess the performance of alternative dosing regimens of Q-Pan H5N1 vaccine using a desirability function that considers immunogenicity by HI/MN assay 21 days after the second dose and fever scores after the first dose and the second dose with as reference half the adult dose [1.9 µg HA with AS03B]. All comparisons are descriptive.

The following tables provide (1) the LL of 95%CI for the GMT ratio based on various assumptions of standard deviation and point estimate of GMT ratio ([Table 21](#)); (2) probability to detect at least one subject with fever  $\geq 38^{\circ}\text{C}$  ([Table 22](#)); (3) power to meet LL of 95% CI for SCR>40% and LL of 95%CI for SPR>70% ([Table 23](#)).

**Table 21 Lower limit of 95%CI for GMT ratio of vaccine group to the reference group 21- days after second vaccination**

	log GMT standard deviation				
	0.50	0.55	0.60	0.65	0.70
GMT ratio	0.25	0.14	0.13	0.13	0.12
	0.29	0.16	0.16	0.15	0.14
	0.34	0.19	0.18	0.17	0.16
	0.4	0.23	0.21	0.20	0.19
	0.5	0.28	0.27	0.25	0.24
	0.67	0.38	0.36	0.34	0.32
	1	0.57	0.54	0.51	0.48

Assumed non-evaluable rate is less than 10%, with a sample size of 34 evaluable subjects per group and SD (log value)=0.60, the LL of 95%CI for the GMT ratio would be 0.25 if the point estimate of GMT ratio of vaccine group to the reference group is 0.5 (50% of GMT value deduction).

**Table 22 Probability to detect fever during 7-day follow-up after vaccination**

Endpoint	Incidence rate	Num of evaluable subjects	at least X subjects with fever	Prob of detecting at least one subjects with fever*
Fever $\geq 38^{\circ}\text{C}$	22.4%	34	1	$\geq 99.9\%$
Fever $\geq 38.5^{\circ}\text{C}$	10.7%	34	1	97.9%

Assumed a binomial distribution

Based on incidence of fever observed in Q-Pan H5N1-021 in that age group, with 34 evaluable subjects per group the probability of observing at least one subject with fever  $\geq 38^{\circ}\text{C}$  is  $>99.9\%$  assuming a fever incidence rate of 22.4%; and the probability of observing at least one subject with fever  $\geq 38.5^{\circ}\text{C}$  is 97.9% assuming the incidence rate of 10.7%.

**Table 23 Power to meet LL of 95% CI for SCR>40% and LL of 95%CI for SPR>70% in one of the vaccine group (without Type I error adjustment)**

Endpoint	Success Criteria	N evaluable in each group	Reference value 	Power 
HI response: SCR	LL of 95% CI > 40%	34	90%	>99.99%
HI response: SPR	LL of 95% CI > 70%	34	90%	75.04%

Key: LL=Lower Limit; SP=Seroprotection (HI antibody titers > 1:40); SPR=Seroprotection rate; CI=confidence interval.

Source of reference values: lower 95% confidence bound of SPR at Day 42 for Q-Pan-021 in children 6-35 months of age receiving 1.9 µg H5N1 HA antigen adjuvanted with AS03B.

PASS 2005 [Miettinen, 1985], 2-sided one proportion test, alpha=5%.

As one of the secondary objectives, HI responses in each vaccine regimen 21 days post dose 2 will be evaluated. The power to meet LL of 95% CI for SCR>40% and LL of 95%CI for SPR>70% is 75.0% in one vaccine group (no type I error adjustment).

## 10.4. Cohorts for Analyses

### 10.4.1. Total Vaccinated Cohort

The total vaccinated cohort (TVC) will include all subjects who received at least one dose of vaccine (TVC cohort for booster safety analysis will include all the subjects who received the booster dose):

- A safety analysis based on the Total vaccinated cohort will include- all vaccinated subjects.
- An immunogenicity analysis based on Total vaccinated cohort will include-all vaccinated subjects for whom immunogenicity data are available.

The total vaccinated cohort analyses will be performed per investigational vaccine actually administered at the first dose.

The analysis of safety will be performed on the TVC.

### 10.4.2. Cohort for according-to-protocol (ATP) immunogenicity analyses

The ATP cohort for immunogenicity analysis will include all vaccinated/eligible subjects:

- who have received all study vaccine dose(s) (3-doses for booster immunogenicity analysis, 2-doses for other analyses) per protocol treatment assignment;
- for whom the randomization code is unbroken during the relevant analysis interval;
- who have not received any investigational or non-registered product (drug or vaccine) other than the study vaccine(s) during the relevant analysis interval;
- who have not received any non-study vaccine during the relevant analysis interval who have not received any immunoglobulins and/or any blood products during the relevant analysis interval

- for whom there was no chronic administration of immunosuppressants) during the relevant analysis interval.
- who develop a physician-confirmed infection with an A/Indonesia/5/2005 (H5N1) virus during the relevant analysis interval.
- who have results available for the relevant *assay* (HI and MN) for all blood samples to be collected during the relevant analysis intervals for ATP-Day 42; for ATP-Day 385 (persistence); for ATP-Day 392 post booster dose (ATP-booster).

#### 10.4.3. Cohort for analysis of the immunogenicity-fever score

The analysis cohort for combined immunogenicity and safety of the two-dose primary series will include all subjects in the ATP cohort for immunogenicity analysis at Day 42 (Section 10.4.2) for whom temperature measurements are available during the first 3 days after both vaccine doses 1 and 2.

Subjects without immunogenicity results at Day 42 or for whom one or more daily temperature measurements are missing during the first 3 days after either vaccine dose [dose 1 or dose 2] will be excluded from the immunogenicity/fever index calculation for the primary series.

